8.2.6. Efficacy Analyses

All efficacy definitions are described in section 6.1.

All efficacy analysis will be based on the Efficacy population. Additional efficacy analyses will be performed on the ITT population.

All primary and secondary endpoints based on radiological (and photographic where applicable) assessments of tumour burden (ORR, CBR, RD, PFS, etc.) will be derived using the local radiologist's/investigator's assessment.

8.2.6.1. Analyses of Primary Endpoint

The primary endpoint is ORR

Objective Response Rate (ORR): A patient will be considered to have achieved an OR if the patient has a sustained complete response (CR) or partial response (PR) according to RECIST v.1.1 definitions. Otherwise, the patient will be considered as non-responders in the ORR analysis. ORR will be estimated by dividing the number of patients with objective response (CR or PR) by the Efficacy population ("response rate").

$$\text{Objective Response Rate} = \frac{\text{Number of CRs + PRs}}{\text{Efficacy population}}$$

The ORR will be reported, including a 95% confidence interval.

These analyses will be conducted at a two-sided 0.05 level of significance.

The number of responders needed at the end of stage 2 to reject the null hypothesis is at least 14 responders.

Additional sensitivity analyses will be outlined in the SAP. For the analysis in the ITT population, patients with inadequate data for tumour assessment (e.g., no baseline assessment or no follow-up assessments) will be considered as non-responders in the OR rate analysis.

In addition, the best objective response for each patient will be summarized.

8.2.6.2. Analysis of Secondary Endpoints

The secondary efficacy endpoints are:

Clinical Benefit Rate (CBR): A patient will be considered to have CB if the patient has a sustained complete response (CR) or partial response (PR), or stable disease (SD) ≥ 24

weeks according to RECIST v.1.1 definitions. Otherwise, the patient will be considered as not achieving CB in the CBR analysis.

CBR will be estimated by dividing the number of patients with CR, PR, or SD \geq 24 weeks by the efficacy population by treatment arm.

$$\text{Clinical Benefit Rate} = \frac{\text{Number of CRs} + \text{PRs} + \text{SD} \geq 24 \text{ weeks}}{\text{Efficacy population}}$$

The CBR will be reported, including a 95% confidence interval.

For the CBR analysis in the ITT population, patients with inadequate data for tumour assessment (e.g., no baseline assessment or no follow-up assessments) will be considered as not achieving CB in the CBR analysis.

Response Duration (RD): RD data will be censored on the date of the last tumour assessment on study for patients who do not have objective tumour progression and who have not died due to any cause while on study. Additionally, patients who start a new anti-cancer therapy prior to documented PD will be censored at the date of the last tumour assessment prior to the start of the new therapy.

RD will only be calculated for the subgroup of patients with an objective response.

Progression-Free survival (PFS): PFS data will be censored on the date of the last tumour assessment on study for patients who do not have objective tumour progression and who have not died due to any cause while on study. Additionally, patients who start a new anti-cancer therapy prior to documented PD will be censored at the date of the last tumour assessment prior to the start of the new therapy.

The analyses of PFS will be performed in the ITT and Efficacy populations. PFS time will be summarized for the ITT population using the Life tables and displayed graphically where appropriate. Confidence intervals (CIs) for the 25th, 50th and 75th percentiles of the event free time will be reported.

Overall Survival (OS): OS data will be censored on the last date the patient is known to be alive.

OS will be analysed in the ITT and Efficacy population. The median event times and 95% CIs will be estimated.

All of the above secondary analyses will be conducted at a two-sided 0.05 level of significance.

The secondary time-to-event endpoints (RD, PFS, OS) will be summarised using a Kaplan-Meier analysis and associated curves.

Additional sensitivity analyses will be outlined in the SAP.

8.2.7. Safety Analyses

The toxicity and tolerability of study drugs/medications will be evaluated in the safety population. Safety analyses will include summaries of the incidence of adverse events by maximum NCI-CTCAE grade (v4.0; NCI 2010) that occur during the study treatment period or within 30 days of the last dose of study treatment, regardless of causality and according to the relationship to study drug/medication as assessed by the Investigator. Additionally, the following safety-related outcomes will be summarized:

- Study treatment discontinuations due to adverse events.
- Deaths.
- SAEs and AESIs
- Hospitalizations and transfusions.
- Use of key concomitant medications or growth factors.

Analyses for data with discrete dates, for example, deaths, transfusions, and concomitant medications, will be done through 30 days after each patient's last dose of study treatment. Adverse events will also be analysed in this timeframe; that is, if an event starts within 30 days of discontinuation from study treatment, but after 30 days after the last dose of study treatment, it will not be included.

Adverse events data and serious adverse events will be presented in frequency tables by grade. Haematological and clinical biochemistry toxicities will be assessed from laboratory test parameters. The safety analysis will be performed in the safety population.

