1.6.1. Important Potential Risks

- Myelodysplastic syndrome (MDS) /acute myeloid leukaemia (AML)**

The incidence of MDS/AML in patients treated in clinical trials with olaparib monotherapy, including long-term survival follow-up, was <1.5 % and the majority of these events have had a fatal outcome. All patients had potential contributing factors for the development of MDS/AML, having received previous chemotherapy with platinum agents. Many had also received other DNA damaging agents. The majority of reports were in germline *BRCA* mutation carriers and some of the patients had a history of previous cancer or of bone marrow dysplasia.

Since bone marrow is known to be a target organ for olaparib toxicity, increased risk of MDS/AML with long-term exposure to olaparib cannot be excluded. However, there is insufficient data at present to evaluate this relationship. Moreover, while non-clinical data suggest bone marrow progenitor cell populations are reduced temporarily following olaparib treatment, there is no evidence to date linking olaparib treatment to the generation of abnormal bone marrow precursors. Furthermore, all patients who developed MDS/AML had extensive prior chemotherapy and while it is not possible to exclude the contribution of olaparib, it must be considered that there were other potential contributing factors in all cases. The risk is perceived as low and not outweighing the potential benefit of study treatment in the breast cancer patients to be included in the current trial.

Clinical guidelines for managing bone marrow toxicity are indicated in Section 5.4. Special Treatment Considerations. Dose Adjustments of Olaparib.

- Pneumonitis**

Pneumonitis events have been reported in <1 % of patients receiving olaparib monotherapy in clinical studies. The reports of pneumonitis had no consistent clinical pattern and were confounded by a number of pre-disposing factors (cancer and/or metastases in lungs, underlying pulmonary disease, smoking history, and/or previous chemotherapy and radiotherapy). When olaparib was used in clinical studies in combination with other therapies there have been events with a fatal outcome.

Investigation of any new or worsening pulmonary symptoms has been implemented as part of the safety management of the study in Section 5.4.2. Management of Non-Haematological Toxicity.

- **New Primary Malignancies other than MDS/AML**

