	
• During treatment with the study drug: during the study, site personnel will record any change in the condition(s) and the occurrence and nature of any adverse events. A CTCAE grade rating will be assigned before each cycle for any adverse event experienced during the previous cycle.• 30-day post- treatment follow-up period: each patient will have a 30-day post-discontinuation follow-up evaluation approximately 30 days following the discontinuation of study treatment. Patients should be closely followed for study treatment adverse events in order to detect delayed toxicity. If drug-related toxicity is present beyond 30 days post-discontinuation, patients must be followed until the toxicity resolves or improved to baseline, the relationship is reassessed as unrelated, the Investigator confirms that no further improvement can be expected, another therapy is initiated, or death.• Long-Term Follow-up Period (after the 30-day post-discontinuation): For Pharmacovigilance purposes and characterization, any case of MDS/AML or new primary malignancy occurring after the 30 day follow up period should be reported to GEICAM whether it is considered a non-serious AE [e.g. non-melanoma skin cancer] or SAE, and regardless of investigator's assessment of causality. Investigators will be asked during the regular follow up for overall survival if the patient has developed MDS/AML or a new primary malignancy and prompted to report any such cases.
--	---

	
documented on the eCRF and immediately reported to GEICAM via the designated transmission method, even if the study has been closed.
 
Otherwise, after study treatment completion (i.e. after any scheduled post treatment follow-up period has ended) there is no obligation to actively report information on new AEs or SAEs occurring in former study patients. This includes new AEs/SAEs in patients still being followed up for survival but who have completed the post treatment follow up period (30 days).

--	--

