Adverse Events of Special Interest (AESIs)	
Adverse events of special interest [AESI] are events of scientific and medical interest specific to the further understanding of olaparib's safety profile and require close monitoring and rapid communication by the investigators to GEICAM. An AESI may be serious or non-serious. Adverse Events of Special Interest for olaparib are the Important Potential Risks of MDS/AML, new primary malignancy (other than MDS/AML) and pneumonitis.
 
ANY event of MDS/AML, new primary malignancy, or pneumonitis should be reported to GEICAM immediately (within 24 hours following knowledge of the event), as per the SAE notification instructions whether it is considered a non-serious AE [e.g. non-melanoma skin cancer] or SAE, and regardless of investigator's assessment of causality.
 
A questionnaire will be sent to any investigator reporting these AESIs, as an aid to provide further detailed information on the event. During the study there may be other events identified as AESIs that require the use of a questionnaire to help characterize the event and gain a better understanding regarding the relationship between the event and study treatment.
 
For information about overdose and medication errors please refers to sections 5.4.4. and 11.1. Overdose.

AST or ALT $\geq 3 \times$ ULN or total bilirubin $\geq 2 \times$ ULN	
Cases where a subject shows an AST or ALT $\geq 3 \times$ ULN or total bilirubin $\geq 2 \times$ ULN could need to be reported as SAEs, please, refer to Attachment 5 ‘Actions required in cases of combined increase of Aminotransferase and Total Bilirubin – Hy’s Law’, for further instructions.

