Events to Collect	AE/SAEs Related to Procedures	New/Ongoing AE/SAEs Regardless of Relatedness to Study Treatment or Procedures		
New/Ongoing SAEs, including sudden death of unknown cause, that the investigators considers there is a reasonable possibility that the event is causally related to the investigational product or protocol procedure, even if the study has been closed
 
Any case of MDS/AML or new primary malignancy whether it is considered a non-serious AE [e.g. non-melanoma skin cancer] or SAE, and regardless of investigator's assessment of causality

Abbreviations: AE = adverse event, ICD = informed consent document, SAE = serious adverse event.

Protocol Attachment 5. Actions required in cases of combined increase of Aminotransferase and Total Bilirubin – Hy's Law

TABLE OF CONTENTS

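### The 30-day limit on adverse event analyses, with no exception for AESIs, leaves late MDS/AML and new primary malignancies that the protocol solicits out of the planned safety results

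*Protocol*

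**What the plan says.** **Analysis.** Protocol 8.2.7 names "SAEs and AESIs" among the outcomes to be summarised and gives that item no time window of its own. The next paragraph sets a limit of 30 days after the last dose for dated data and continues: "Adverse events will also be analysed in this timeframe". It illustrates the limit with an event that starts within 30 days of discontinuation "but after 30 days after the last dose of study treatment, it will not be included". SAP 9.2.2 repeats both passages. Neither document makes an exception for AESIs.

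**Definition.** Protocol 6.2.4: "Adverse Events of Special Interest for olaparib are the Important Potential Risks of MDS/AML, new primary malignancy (other than MDS/AML) and pneumonitis". AESIs are thus a subset of adverse events.

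**Collection.** Under the long-term follow-up heading, Protocol 6.2.3 requires that "any case of MDS/AML or new primary malignancy occurring after the 30 day follow up period should be reported to GEICAM", whether serious or not and whatever the causality. It makes this an active enquiry: "Investigators will be asked during the regular follow up for overall survival if the patient has developed MDS/AML or a new primary malignancy". Attachment 4 lists the same two event types for the long-term period, together with SAEs judged causally related. Protocol 6.2.4 also requires related SAEs to be reported whatever their timing. Pneumonitis is not named for the long-term period.

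**Background.** Protocol 1.6.1 gives the MDS/AML incidence on olaparib monotherapy: "including long-term survival follow-up, was <1.5 % and the majority of these events have had a fatal outcome".

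**The concern.** The collection rules and the analysis rules do not meet. Sites are asked about two event types until death or data cut-off, but the written analysis stops 30 days after the last dose. A patient with MDS or a second cancer some months after stopping olaparib would be in the database and in the sponsor's pharmacovigilance files, yet would not be counted in the AESI summary that both documents promise.

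The summary could then show no MDS/AML although a case had been reported. A rate cut at 30 days would also not be like for like with the background figure in Protocol 1.6.1, which counts long-term follow-up. Safety is a secondary objective, and in a trial of at most 34 patients one case is 1/34 = 2.9%, so one omission changes what the table shows.

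**Working it through.** The plan states no figure on this point, so there is none to reproduce. The check is a comparison of texts, followed by an illustration of scale.

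**Texts side by side**

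- MDS/AML and new primary malignancy: solicited after day 30 (Protocol 6.2.3, Attachment 4), but outside the analysis window (Protocol 8.2.7, SAP 9.2.2).
- Drug-related SAEs: reportable at any time (Protocol 6.2.4, Attachment 4), but outside the analysis window after day 30.
- Pneumonitis: an AESI, but not solicited after day 30. Protocol 6.2.3 says that, apart from the listed exceptions, there is no duty to report new events actively after the 30-day period.
- SAP section 10: tables 3.1.1 to 3.1.11 are treatment-emergent tables, 3.1.12 covers laboratory events, and 3.2.1 is all-cause mortality. No AESI table or post-window table is named.

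**Scale (illustrative)**

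Inputs:
- n = 34, the maximum enrolment (Protocol 8.1.1).
- MDS/AML rate p below 1.5% (Protocol 1.6.1); 0.5% is used as a lower assumption.
- Median OS 12 months (Protocol 3.2).
- Median time on treatment, assumed equal to median PFS values quoted for olaparib in breast cancer: 54 days and 3.68 months (Protocol Table 4) and 7.0 months (OlympiAD, Protocol 1.4.5.1).

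Step 1. Expected MDS/AML cases at any time, at the ceiling: 34 × 0.015 = 0.51.

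Step 2. Share of survival time after the window, with exponential times (mean = median / ln 2): share = 1 − (mean treatment time + 1 month) / mean OS. Mean OS = 12 / ln 2 = 17.31 months.

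| Median treatment time | Mean | Share after window |
|---|---|---|
| 54 days (1.77 months) | 2.56 months | 1 − 3.56/17.31 = 0.79 |
| 3.68 months | 5.31 months | 1 − 6.31/17.31 = 0.64 |
| 7.0 months | 10.10 months | 1 − 11.10/17.31 = 0.36 |

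Step 3. Omitted cases, assuming a constant hazard over survival time: expected number = 34 × p × share; chance of at least one = 1 − (1 − p × share)^34.

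| p | Share | Expected omitted | Chance of at least one |
|---|---|---|---|
| 1.5% | 0.36 | 0.18 | 17% |
| 1.5% | 0.79 | 0.40 | 33% |
| 0.5% | 0.36 | 0.06 | 6% |
| 0.5% | 0.79 | 0.13 | 13% |

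New primary malignancies (under 1% in Protocol 1.6.1) would add to this and are not included.

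**The case against.** **The AESI item carries no window, and the exclusion sentence describes a narrow case.** Both observations are correct. The sentence before it, however, applies the 30-day limit to adverse events generally, and AESIs are adverse events. At best the text is ambiguous, and the SAP repeats it without resolving it.

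**Late reports are collected for pharmacovigilance.** This stands in part. Protocol 6.2.3 gives pharmacovigilance and characterisation as the purpose. Cases reach the sponsor within 24 hours, a questionnaire follows, serious cases enter the safety-reporting route, and a fatal case counts in OS. A reader might infer that the benefit-risk conclusion would be distorted. The documents do not support that: the events are missing from a descriptive summary, not from the data or from safety oversight, and no decision rule depends on the summary.

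**The table shells may hold an AESI listing.** They are a separate attachment that was not available, so this cannot be ruled out. Such a listing would still conflict with the written limit.

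**A 30-day window is reasonable, because later events may be confounded by subsequent therapy.** This stands for general adverse events. It does not explain soliciting two named event types and then not presenting them.

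**The size is easily overstated.** This stands. At the ceiling, 1 − 0.985^34 = 40%, but that is the chance of any MDS/AML case at any time, not of an omitted one. Protocol 1.6.1 describes a mostly fatal course for MDS/AML only, not for new primary malignancies. It also says that most reports came from germline BRCA carriers, whom this trial excludes, and that all affected patients had received platinum, which this trial does not require.

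**Conclusion.** The point holds on the text of both documents. As written, late MDS/AML and new primary malignancies are collected and then left out of the planned safety results, and the resulting MDS/AML rate could not be compared with the protocol's background figure.

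The likely number is small: about 0.18 to 0.40 omitted MDS/AML cases at the 1.5% ceiling (a 17% to 33% chance of at least one), or a 6% to 13% chance at 0.5%. These figures rest on exponential times, a constant hazard, a median OS of 12 months, treatment time equal to the quoted PFS medians, and full enrolment. Three things would lower them: the exclusion of germline carriers, stopping after stage 1, and the data cut-off, since the calculation runs survival to death. A hazard that rises after treatment would raise them. The mismatch itself depends on none of these numbers.

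A reader might extend the point to pneumonitis. The documents do not support that: it is not solicited after day 30, so a cumulative count would look complete without being so.

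**What to change.** In Protocol 8.2.7 and SAP 9.2.2:

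- Exempt MDS/AML and new primary malignancy from the 30-day rule. List or summarise them from first dose to data cut-off, with time since last dose, separately from treatment-emergent events.
- List drug-related SAEs reported after day 30, which the protocol already requires sites to report.
- Keep the 30-day window for all other adverse events, including pneumonitis not reported as a drug-related SAE.
- Add the listing to SAP section 10 and to the shells.

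The cost is a short addition to each document and one extra listing of data already collected; sample size and alpha are unaffected. The drawback is that late events may reflect subsequent therapy. The listing should say so and show the therapies received after olaparib, which the protocol already collects.

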8.2.7.1. Other significant adverse events (OAE)

During the evaluation of the AE data, GEICAM qualified experts will review the list of AEs that were neither reported as SAEs nor AESIs. Based on the expert's judgment, significant adverse events of particular clinical importance may, after consultation with the Global Patient Safety Physician, be considered OAEs and reported as such.

A similar review of laboratory, vital signs or ECG data will be performed for identification of OAEs. Examples of these are marked haematological and other laboratory abnormalities, and certain events that lead to intervention (other than those already classified as serious), dose reduction or significant additional treatment.

There are currently no identified OAEs for olaparib

8.2.8. *BRCA1/2 Methylation and expression analysis*

To explore changes in the methylation status of *BRCA1/2* promoter in germline DNA prior and after treatment discontinuation.

The methylation status of the *BRCA1* and 2 promoters will be measured in germline DNA from blood cells at the beginning of the study and after disease progression or at the end of

study treatment for other cause, and in paired primary and metastatic lesions. Methylation status will be provided as a continuous (the methylation value will be obtained from the average of the CpG dinucleotides included in the sequence analysed) and also as a binomial variable (status methylated or not methylated).

If methylation status is a continuous variable, to compare the value of methylation between prior and after treatment, the difference of these values will be used and will be used statistical t (student-Fisher) or Wilcoxon test depending if it must be used a parametric or non-parametric test.

If methylation status is a binomial variable, to compare the value of methylation between prior and after treatment it will be used the McNemar test or exact binomial test.

To correlate germline *BRCA1/2* methylation data with efficacy parameters:

To evaluate the effect of methylation status with time to event variables (e.g. PFS, OS) it will be used a univariate Cox Regresion model.

To evaluate the effect of methylation status with efficacy rate parameters it will be used chi-square test if both of them are quantitative, and will be used an ANOVA analysis if one variable is quantitative and the other one is qualitative.

To correlate *BRCA1/2* methylation between germline and somatic DNA:

To compare the continuous values of germline and somatic DNA methylation, the difference of these values will be used and it will be used statistical t (student-Fisher) or Wilcoxon test depending if it must be used a parametric or non-parametric test.

To correlate *BRCA1/2* methylation between primary tumour and metastatic lesions:

If *BRCA1/2* in metastatic lesions is a continuous variable, to compare the value of *BRCA1/2* between primary tumour and metastatic lesions, the difference of these values will be used and it will be used statistical t (student-Fisher) or Wilcoxon test depending if it must be used a parametric or non-parametric test.

To correlate *BRCA1/2* expression with efficacy parameters:

mRNA levels of *BRCA1* and *2* will be assessed in blood and available tumour samples. Expression data will be given as a continuous or as a binomial variable.

To evaluate the effect of *BRCA1/2* expression with time to event variables (PFS, OS) it will be used a univariate Cox Regresion model.

To evaluate the effect of *BRCA1/2* expression with efficacy rate parameters it will be used chi-square test if both of them are quantitative, and will be used an ANOVA analysis if one variable is quantitative and the other one are qualitative.

To correlate *BRCA1/2* expression with *BRCA1/2* promoter methylation status:

We will compare *BRCA1/2* expression and *BRCA1/2* promoter methylation status when they are binary data using chi-square test.

If methylation status and expression data are given as continuous variables, they will be compared using statistical t (student-Fisher) or Wilcoxon test depending if it must be used a parametric or non-parametric test.

If appropriate, additional analysis on all these biomarkers may be performed. More detail of all the Analysis of Secondary Endpoints will be described in the SAP.

8.2.9. *Other Analysis*

8.2.9.1. *Other Biomarker Analysis*

For baseline continuous endpoint data, descriptive statistics, including the mean, standard deviation, median, minimum, and maximum values, will be provided.

For baseline categorical data, the number and percentage of patients in each category will be provided.

Appropriate statistical methods will be used to investigate any possible relationship of biomarker levels with olaparib anti-tumour efficacy. If appropriate, additional exploratory analysis on biomarkers may be performed.

8.2.9.2. *Subgroup Analyses*

Exploratory subgroup analysis may be performed if deemed appropriate.

8.2.10. *Interim Analysis*

There is no planned any interim analysis.

The optimal two stage Simon Model is carried out in two steps. The purposes of the step 1 analysis is to allow early stopping of the study for futility.

Following the two-stage Simon design, it will be reviewed whether 4 of the first 12 evaluable patients show tumour response according to RECIST v.1.1, and if this occurs, additional patients will be included to get a total of 34 patients.. If 3 or less than 3 patients of the first 12 evaluable patients show an OR, recruitment will be stopped.

8.2.11. *Criteria for End of Study*

This study will be considered complete following the data cut-off date and datalock for the final analysis. The data cut-off date for the final analysis will occur after all enrolled patients have died or withdraw of the informed consent or there is sufficient data to achieve the primary and secondary objectives, whatever occurs first. It is estimated that the final analysis could be performed approximately 30 months after the enrolment of the first patient because, considering a median OS of 12 months, it is estimated that more than 50% of death events will have occurred at that time and overall survival analysis could be performed. If further data are collected that are not included as part of the final locked

database, the post-lock data will eventually be combined with the locked database and stored in a data library separate from the locked database.

Performing exploratory objectives will be independent of the date of the end of the study.

9. Informed Consent, Confidentiality, Responsibility Insurance and Regulatory Considerations

